$\eta = \log(p_{ijk} / (1 - p_{ijk})) = \beta_0 + \beta_1 X_{ijk} + FU_{jk}$, where FU_{jk} is a random effect associated with facility and unit.

The formula for the sample size per group using the method of Diggle is:

$m^* = (z_{\alpha} \sqrt{2PQ} + z_{\beta} \sqrt{p_0 q_0 + p_1 q_1})^2 (1 + (n-1)\rho) / (n(p_1 - p_0)^2)$; and using the GEE method:

$m^* = \frac{(Z_{1-\alpha/2} + Z_{1-\beta})^2 (\pi_1 p_0 (1 - p_0) + \pi_0 p_1 (1 - p_1)) (1 + (n-1)\rho)}{2n\pi_0\pi_1(p_0 - p_1)^2}$. The formula below is adjusted with variance inflation factor (V_{if}) and reliability(R_{el}): $m = V_{if}m^* / R_{el}$ and

$$V_{if} = (1 + (n_e - 1)\rho_e)(1 + (n_s - 1)\rho_s n_e p_e / (1 + (n_e - 1)\rho_e))$$

where $n_s = 5$ is the average number of units in the facility, $\rho_s = 0.015$ is the ICC for facility, $n_e = 17$ is the average number of residents in the unit, $\rho_e = 0.03$ is the ICC for unit, and the reliability:

$$R_{el} = 0.95.$$

The following table assumes $\alpha = 0.05$, power $(1 - \beta) = 80\%$, $R = 0.95$ and $V_{if} = 2.5$ (With $n_e = 17$,

$ICC_{Unit} = 0.03$, $N_s = 5$, $ICC_{Facility} = 0.015$, the fall rate at follow-up: $p_0 = 33\%$ and $p_1 = 20.75\%$). Two

scenarios for ρ (the average correlation of the outcomes over waves) were posited:

Group	Fall rate P(y=1)				Diggle Method		GEE Method	
	Baseline Rate	6 Month	12 Month	Combined 6M & 12M	M ($\rho = 0.5$)	M ($\rho = 0.6$)	M ($\rho = 0.5$)	M ($\rho = 0.6$)
Intervention	37%	22%	19.5%	20.75%	404	431	399	425
Usual Care	37%	34%	32%	33%	404	431	399	425

As shown, with 525 per group, power is adequate for intent-to-treat (ITT) analyses, including all respondents. Because randomization is at the facility rather than individual level, there is the potential for imbalance on baseline variables and missing covariate data. Assuming attrition of

15% at wave 1, it is estimated that 445 per group will have at least baseline and one additional wave of data included, using the EM missing data algorithm; thus, power is adequate to detect the posited difference in fall reduction of about 12% even with attrition.

Recruitment

All residents are approached and invited to participate. For those who do not wish to be interviewed, a different or the same interviewer approaches again at another time that may be more amenable to the resident. All resident questions are addressed and interviews occur at a time and place preferred by the resident.

Assignment of interventions: allocation

Sequence generation

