Analyses for the primary hypothesis for the distal outcome: The primary analyses will examine, on an ITT basis, the differences between the usual care and intervention groups in the reduction of falls/accidents/injuries over time. Other approaches, e.g., the analysis of the “as treated” sample can result in biased estimates of the causal treatment effect due to compromised random assignment. Our primary approach to analyses is guided by our own experience,⁵⁷ and reviews.^{58,59} Depending on the level of missing data, analytic strategies (see below) can be used to address non-compliance, e.g.⁶⁰ Based on prior trials that we have coordinated, sampled from this population, 1 year attrition is between 30% and 40%; thus for 6-month data (projected attrition of 15%), the ITT analyses of all subjects will be feasible. Longitudinal analyses will include those with at least baseline and one follow-up. Sensitivity analysis will be performed using multiple imputation under different assumptions for missing data.

Because randomization is at the facility rather than individual level, imbalance may be observed on baseline variables. Preliminary analyses will be performed to determine whether the groups are balanced. Two-tailed tests of significance will be performed. Binomial tests are to be conducted on dichotomous variables, Poisson tests on nonbinomial (e.g., count) data, and *t* tests on ordinal data, adjusting standard errors for clustered data within facilities; *p* values are reported because the design does not permit randomization at the level of the individual.

Effect on likelihood of falls/injuries/accident reduction:

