Based on prior experience with the outcomes, it is not expected that transformations will be necessary. Baseline variables will be examined by study arm; however, no p values will be provided, and covariates (other than baseline values) are not proposed for inclusion in the main analyses of treatment effects.

Examination of potential region differences: Data from regions (upstate and downstate) will be combined and each outcome (e.g., depression, affect) modeled as a function of two factors (i) intervention, a factor with 2 levels and (ii) region, a factor with 2 levels, and the interaction between (i) and (ii). MEMs will be used for each outcome, e.g., depression, and likelihood ratio tests (χ^2) used to test for significance of the interaction term. The study is not powered to detect meaningful regional differences in treatment effect; therefore we will use $\alpha=0.15$ as a criterion, and explore if regional differences are related to differences in intervention effects.

Interim analyses

There are no plans for interim analysis or predetermined stopping guidelines.

Methods for additional analyses (e.g. subgroup analyses)

Heterogeneity of Treatment Effects (HTE): Because there is interest in examining subgroups to determine for which individuals interventions may be effective, we will perform descriptive HTE with potential effect modifiers as interaction terms. HTE will be examined for subgroups, e.g., those with and without cognitive impairment.

Methods in analysis to handle protocol non-adherence and any statistical methods to handle missing data

Examination of baseline differences on key variables between completers and those lost-to-follow-up will be conducted to inform about the nature of the missing data. The ITT analyses performed using MEMs will permit all individuals with at least one post-baseline observation to be included.

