Depending on the level of missing data, analytic strategies can be used to address non-compliance, e.g.⁷⁵ For the sustainability analyses, analyses will be of those with at least baseline and one follow-up. Sensitivity analysis will be performed using multiple imputation under different assumptions for missing data. Examination of baseline differences on key variables between completers and those lost-to-follow-up will be conducted in order to inform about the nature of any missing longitudinal data. Methods of examining missing data, e.g., propensity scores, inverse probability, EM algorithm and multiple imputation sensitivity analyses will be considered. If substantial missing outcome data are observed, we will use a specific imputation approach, e.g., Markov Chain Monte Carlo procedures⁷⁶ depending on the amount and pattern of missing data. SAS Proc Multiple Imputation and MIAnalyze will be used. We will perform joint simultaneous imputation; at least 50 multiple imputations will be generated and PROC MIAnalyze will be used to combine the results and estimate the log-odds, adjusted standard errors, and significance.

Plans to give access to the full protocol, participant level-data and statistical code

There are no such plans at this time.

Oversight and monitoring

Composition of the coordinating centre and trial steering committee

The DCC at the RD-HHAR is responsible for oversight of data collection and analyses.

Composition of the data monitoring committee, its role and reporting structure {21a}

The Data Safety and Monitoring Board (DSMB) or data monitoring committee (DMC) is composed of five members including a chair, clinician/ safety officer, and a biostatistician. The NIA project

officer will also attend DSMB meetings. The DSMB responsibilities include: review the research protocol, informed consent documents and plans for data safety and monitoring; evaluate the progress of the trial, including periodic assessments of recruitment, accrual and retention, participant risk versus benefit, performance of the trial sites, and other factors that can affect study outcome; review study performance, make recommendations and assist in the resolution of problems reported by the principal Investigator; protect the safety of the study participants; report to NIA on the safety and progress of the trial; and ensure the confidentiality of the study data and the results of monitoring. The Board acts independently from the study sponsor.

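### Does the plan leave the ITT set for the falls comparison, and the falls of residents who leave, too loosely defined?

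*Combined protocol and SAP*

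**What the plan says.** Five places bear on who is analysed.

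- **Sample size.** With 525 per group, "power is adequate for intent-to-treat (ITT) analyses, including all respondents". After 15% attrition, "it is estimated that 445 per group will have at least baseline and one additional wave of data included", with the EM algorithm named for missing data.
- **Statistical methods, primary hypothesis.** The analysis is on an ITT basis. For the 6-month data, with 15% projected attrition, "the ITT analyses of all subjects will be feasible". The next sentence reads "Longitudinal analyses will include those with at least baseline and one follow-up", followed by "Sensitivity analysis will be performed using multiple imputation under different assumptions for missing data".
- **Methods for non-adherence and missing data.** The ITT mixed models "will permit all individuals with at least one post-baseline observation to be included". Shortly after: "For the sustainability analyses, analyses will be of those with at least baseline and one follow-up". Imputation is then detailed: "at least 50 multiple imputations will be generated and PROC MIAnalyze will be used to combine the results and estimate the log-odds". A comparison of completers with those lost is planned, and inverse probability methods are to be considered.
- **Retention.** Expected attrition is 15% at 6 months and up to 40% at 12 months. Follow-up invitations go to enrolled residents still living in the facility.
- **Outcomes, Chart data, Accident/Incident Reports.** Falls also come from charts and incident reports, which are reviewed to the end of the study. The outcome is treated both as any fall and as a count.

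The primary model is a mixed logistic regression adjusted for baseline falls, with random effects for facility, unit and subject.

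**The concern.** An ITT label normally implies everyone enrolled in the randomised facilities, here 525 per arm. The working rule looks like 445, so about 80 residents per arm (15%) would drop out of a comparison that claims to keep them. The labels also vary: respondents, subjects, longitudinal, sustainability, post-baseline observation.

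The fall records sharpen the point. A resident who falls in month 3 and leaves in month 4 may have a recorded outcome event but no follow-up wave. The plan does not say whether that event counts, which wave it belongs to, or what time at risk applies. The logistic model has no exposure term, and no offset is stated for the count. If exit differed by arm in a way tied to fall risk, the estimate could be biased. If the set were settled after the data were seen, there would be room for choice.

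**Working it through.** **1. The plan's own figures.** Inputs from the Sample size section: p0 = 0.33, p1 = 0.2075, two waves, variance inflation 2.5, reliability 0.95, power 80%; two-sided 5% from Statistical methods. The Diggle formula gives 153.30 × 2.5/0.95 = 403.4 (ρ = 0.5) and 163.52 × 2.5/0.95 = 430.3 (ρ = 0.6). The GEE formula gives 398.0 and 424.5. The plan's 404, 431, 399 and 425 all reproduce. The number after attrition is 525 × 0.85 = 446.25, against the stated 445.

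**2. The wording side by side.** The longitudinal rule, the sustainability rule, the post-baseline rule for the mixed models and the count of 445 all require baseline plus at least one later observation. The sustainability sentence carries the same rule as the longitudinal one under another label. The phrase about all subjects is limited to the 6-month data, and all respondents can simply mean those who responded. These are not four different sets.

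**3. Size of the set under each reading, per arm.** Leavers before month 6: 525 × 0.15 = 78.75. Assume that the table's 34% and 22% are six-month risks (the documents do not say so), with constant hazard and exit at mid-window. Risk before exit is then 1 − 0.66^0.5 = 0.1876 (usual care) and 1 − 0.78^0.5 = 0.1168 (intervention).

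| Reading | Usual care | Intervention |
|---|---|---|
| A follow-up wave is needed | 446 | 446 |
| A leaver's recorded fall also qualifies | 446.25 + 14.8 = 461 | 446.25 + 9.2 = 455 |
| All enrolled | 525 | 525 |

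**4. Effect on the odds ratio with the plan's rates.** Reference: (0.22/0.78)/(0.34/0.66) = 0.548.

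- Leavers enter only because they fell: (0.85×0.34 + 0.15×0.1876)/(0.85 + 0.15×0.1876) = 36.1%, and (0.85×0.22 + 0.15×0.1168)/(0.85 + 0.15×0.1168) = 23.6%. The odds ratio is 0.546.
- Fallers leave more often, equally in both arms: each arm's odds are multiplied by (1 − qf)/(1 − qn), where qf and qn are the exit probabilities of fallers and non-fallers. The factor cancels, so the ratio stays at 0.548. With qn = 0.10 and qf from 0.20 to 0.40, exit differs between arms by only 0.12 × (qf − qn) = 1.2 to 3.6 points.

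**5. Illustration with inputs not in the documents.** No true effect, risk 34%, and leavers at k times stayers' risk, so stayers' risk is 0.34/(1 − e + k·e) at exit proportion e.

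- Exit 12% v 18%, k = 1.5: 32.1% v 31.2%, odds ratio 0.960 (1.042 with the arms reversed).
- Exit 10% v 20%, k = 2.5: 29.6% v 26.2%, odds ratio 0.844 (1.185 reversed).

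With baseline rate 37%, follow-up 34% and correlation 0.5, adjustment for baseline falls returns the first case to 1.000 if exit depends only on baseline falls. It leaves 0.960 if exit depends only on follow-up falls. The second case cannot arise from baseline falls alone. It needs leavers' risks of 2.5 × 0.2957 = 73.9% and 2.5 × 0.2615 = 65.4%. Risk among baseline fallers is at most [0.37×0.34 + 0.5√(0.37×0.63×0.34×0.66)]/0.37 = 64.9%.

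On the absolute scale, if the 15% who leave had the same risk in both arms, the all-enrolled difference would be 0.85 × 12.25 = 10.4 points. With leavers at 50% v 35% it would be 10.4 + 0.15 × 15 = 12.7. The choice of set can move the estimate either way.

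**6. Power.** If all 445 supply both waves, power is Φ(2.802 × √(445/M) − 1.960), which is 84.1% for M = 399 and 81.2% for M = 431. If 40% are lost by month 12, 315 have both waves and 131.25 have one. Information in single-wave equivalents is 315 × 2/(1 + ρ) + 131.25 = 551.25 (ρ = 0.5) or 525.0 (ρ = 0.6). Multiplied by 0.95/2.5, this gives effective sizes of 209.5 and 199.5, with power of 81.0% and 79.0%.

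**7. The obvious addition.** A Poisson model of recorded falls in all enrolled residents, with an offset for time in residence, would rest on records made by staff who know of the training, and Module 3 covers reporting guidelines. An assumed 5% to 10% relative difference in recording moves the rate ratio by 5% to 10%. The exit bias illustrated in step 5 corresponds to rate ratios of 0.97 to 0.88, that is 3% to 12%.

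**The case for a change.** The strongest case for a change is that imputation, as planned, is a sensitivity analysis. It neither defines the primary set nor says what becomes of falls actually observed. A mixed model uses the outcome rows it is given, and whether a leaver's record forms a row is exactly what is unstated. Attrition of 15% rising to 40% touches many residents, and a sentence in the SAP costs little. The larger group with part-observed time is also missing from the set sizes above: about 131 per arm expected to leave between months 6 and 12.

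Of this, the narrow gap stands: there is no rule for partial windows or for falls recorded before exit. It is also fair that power is not wholly untouched, since 79.0% at ρ = 0.6 is just under the 80% target. But that comes from loss at month 12, which better wording of the set would not recover. What does not stand is the picture of four competing sets or of a demonstrated bias. Chart and incident-report collection is not limited to current residents; the restriction in the Retention section governs follow-up invitations. A stricter definition would also leave the primary model as it is. If a leaver must have a completed window to count, falls in an incomplete window still stay out of it.

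**Conclusion.** No change is needed. The plan's inclusion rules amount to one set, residents with baseline and at least one follow-up, about 445 of 525 per arm. The stray labels are slips of wording. How a partial window is coded is a derivation detail that analysts can settle sensibly within the planned mixed logistic model, with the planned imputation and completer comparison to show whether exit matters.

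On the plan's own rates, the treatment of leavers shifts the odds ratio from 0.548 to 0.546 at most in the cases checked. That rests on six-month risks of 34% and 22%, constant hazard and mid-window exit. Values as far out as 0.844 or 1.185 require arm differences in exit and leaver risks that were assumed for illustration, and the documents give no reason to expect either direction. The added recorded-falls model offers no clear gain, because its plausible ascertainment bias is of similar size. The attrition the plan expects by month 12 puts approximate power at 79% to 81%, whichever label the set carries.

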The Feeling Tone Questionnaire (FTQ): The FTQ measure of affect contains 16 questions asked of the resident. Typical items are: "Are you feeling well?"; "Are you feeling happy today?"; "Do you feel lonely?". Each item is coded "yes", "no" or "equivocal (sometimes, it depends)", and the response rated for affect using a 5-point continuum from 1 -- "laughs, praises, enthusiastic, emphatically positive" to 5 -- "extreme negative -- cries, groans, curses, is emphatically negative". Three scales are scored: Response, Affect and Total. The FTQ has been used among numerous samples of nursing home residents, in which reliabilities were in the 0.90's. In an AL sample alphas

ranged from 0.73 to 0.90 at baseline and from .77 to 0.93 at follow-up. The measure has recently been evaluated and shortened²⁸ using a large sample of 6000 LTSS residents, including AL.

Performance Activities of Daily Living (PADL): The PADL²⁹ (alpha typically in the 0.90's)³⁰ is a 27-item scale that measures an individual's lack of ability to perform various upper and lower body movement tasks associated with eating, dressing and grooming, such as putting on a sweater, buttoning and unbuttoning a sweater, guiding a spoon to the mouth, combing hair independently. Performance times are recorded, and items are rated as to whether the task was performed with or without cueing, or could not be performed at all.

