Statistical models: The primary endpoint analysis for comparison between the two groups with respect to various outcomes will be based on models for the outcome at 6 and 12 months as a function of the intervention condition, adjusting for the baseline value of the outcome, i.e. an ANCOVA-type MEM analysis with intervention as a factor with two levels and baseline value as a covariate. For multiple outcomes (e.g. NIH PROMIS and FTQ) MANCOVA-type MEMs will be used to simultaneously model the multiple outcome variables. An additional factor (domain) denoting the individual outcome variables will be included in the model together with interactions between domain (depression/affect measures) and intervention. A significant interaction term would indicate that the effect of the treatment is different for affect and depression; in that case two treatment effects will be estimated for each outcome. If the interaction is not significant a model with only main effects for depression/affect and treatment will be fit and the (common) treatment effect will be estimated from this model. In addition to significance testing, we will estimate the treatment effects with 95% CI. The MEMs allow modeling the correlation between the variables assessed on the same subject and that between subjects from the same units and facilities. Group differences in total scores will be examined using a linear mixed (fixed and random effects) model for effect estimation.

The use of SAS Proc MIXED will allow for the possible group heterogeneity in residual variances that may require modeling to satisfy model assumptions and improve model fit, and the modeling of the covariance structure. In secondary analyses, we will examine within subjects change over time. We did not perform power calculations for the secondary outcomes because the most

stringent power requirements are for the primary outcome. However, we will be able to detect relatively small effect sizes, given the sample size.

Examination of the exploratory potential mediating effects of behavior on the relationship between the R-REM intervention and the falls/injuries/accident outcome will be examined using mediation analyses. Although recent evidence from Monte Carlo studies support simple joint significance tests of the mediating path coefficients,^{70,71,72} also examined will be other formal tests of mediation effects.^{73,74}

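### The joint FTQ and PROMIS model pools to one common effect on a non-significant interaction, with no common scale or direction specified, so both the test and the pooled estimate can depend on units

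*Combined protocol and SAP*

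**What the plan says.** The rule is in the Statistical models section of the combined protocol and SAP. For multiple outcomes, with PROMIS and FTQ as the example, "MANCOVA-type MEMs will be used to simultaneously model the multiple outcome variables". A domain factor and its interaction with intervention are added. The plan reads the test as follows: "A significant interaction term would indicate that the effect of the treatment is different for affect and depression". The consequence of significance is a split by domain, although its wording, "in that case two treatment effects will be estimated for each outcome", presumably means one effect per outcome. The opposite result removes the interaction term: "If the interaction is not significant a model with only main effects for depression/affect and treatment will be fit". What the plan then reports is a single pooled number, because "the (common) treatment effect will be estimated from this model".

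On the scores themselves:

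- **FTQ.** "The FTQ measure of affect contains 16 questions asked of the resident", with "the response rated for affect using a 5-point continuum from 1" (positive) to 5 (negative). Three scores are listed (Response, Affect, Total). The plan does not say which enters the model, or whether it is a sum or an item mean.
- **PROMIS depression.** It is named under Extended Interview without form, range, direction or SD. About 70% to 80% of residents are expected to receive that interview.
- **Scaling.** No standardisation step appears. The end of the Statistical models section says "it is not expected that transformations will be necessary".
- **Test level and power.** No alpha is given for the domain interaction; the relaxed 0.15 applies to the region interaction only. No power was calculated for the secondary outcomes.

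**The concern.** The domain-by-intervention term compares two treatment effects in score points, and the main-effects model assumes that those point differences are equal. If the two scores are not on one metric, equality in points is not equality of effect. Multiplying one score by a constant changes both the test and the pooled estimate, although the data hold the same information. If the scales ran in opposite directions, two genuine benefits would partly or wholly cancel.

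The rule also treats a non-significant test as support for a single effect. Affect is the first secondary hypothesis. At stake is whether its headline result is one effect or two, and what a single effect would mean.

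**Working it through.** The plan gives no figure for this joint analysis, so there is none to reproduce.

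**Inputs from the document (Sample size section).** 445 analysable residents per group (525 × 0.85 = 446, given as 445); variance inflation 2.5, derived for falls; two-sided alpha 0.05, which the plan does not state for this particular test. Effective n per arm = 445/2.5 = 178.

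**Assumptions.** SD ratio k (larger to smaller SD), correlation r between the scores, and the same true standardised effect d on both. Set the smaller SD to 1.

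**1. Interaction test with equal standardised effects.** The difference in raw effects is d(k − 1), with SE = √[(1 + k² − 2rk) × 2/178].

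With r = 0.5, d = 0.3 and k = 2: difference 0.30; SE = √(3 × 2/178) = 0.184; z = 1.63; two-sided rejection 37%.

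| SD ratio k | d = 0.3 | d = 0.2 | d = 0.1 |
|---|---|---|---|
| 1 | 5% | 5% | 5% |
| 1.2 | 8% | 6% | 5% |
| 1.5 | 19% | 11% | 6% |
| 2 | 37% | 19% | 9% |

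If 75% of residents have PROMIS (effective n = 133.5), the d = 0.3 figures at k = 1.5 and k = 2 fall to about 15% and 29%.

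**2. Weight of the larger-SD scale in the common effect.** This depends on a covariance structure that the plan leaves open.

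- *Domain-specific variances:* weight = (1 − rk)/(1 + k² − 2rk). At r = 0.5 and k = 1.5 this is 0.25/1.75 = 14%. At r = 0.5 and k = 2 it is 0/3 = 0%. At r = 0.6 and k = 2 it is −0.2/2.6 = −8%. The smaller-SD scale dominates.
- *Common residual variance with a resident random effect, complete data:* each raw effect has weight one half. With equal standardised effects, the larger-SD scale supplies k/(1 + k) of the estimate: 60% at k = 1.5 and 67% at k = 2. The larger-SD scale dominates.

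**3. Same data, two FTQ scorings.** Assume PROMIS SD 10, r = 0.5, an FTQ effect of −0.40 SD and a PROMIS effect of −0.10 SD, so −1.0 point on PROMIS.

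- *16-item sum, SD 8:* FTQ effect −3.2; difference −2.2; SE = √[(64 + 100 − 80) × 2/178] = 0.972; z = −2.26. Two effects are reported.
- *Item mean, SD 8/16 = 0.5:* FTQ effect −0.2; difference +0.8; SE = √[(0.25 + 100 − 5) × 2/178] = 1.034; z = +0.77. One effect is reported.
- *Both in SD units:* difference −0.30; SE = √(2/178) = 0.106; z = −2.83, whichever scoring is used.

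The pool-or-split decision changes with a scoring choice that the plan does not make.

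**4. What standardising does not cure.** For a true domain difference of 0.2 SD, SE = √[2(1 − r) × 2/178]. At r = 0.3, z = 0.2/0.125 = 1.59, power 36%. At r = 0.7, z = 0.2/0.082 = 2.44, power 68%. A non-significant test still says little about equality.

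**The case against.** The strongest reply is that the document never says the scores are stacked raw. The sentence on transformations may concern distributional shape only, and no range or SD is given for PROMIS. If the chosen scores had similar SDs and the same direction, the problem would be small: 8% rejection at a ratio of 1.2. This stands. A reader might infer that the plan commits to raw scores with different ranges; the document supports only the statement that no common scale or direction is specified.

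A reader might also infer that the smaller-SD instrument takes over the pooled result. That needs domain-specific variances. The plan mentions possible heterogeneity of residual variances between groups and modelling of the covariance structure, but does not fix it by domain. With a common residual variance the dominance reverses. What survives is that the result depends on units, not that a particular instrument wins.

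The percentages rest on assumed SDs, correlation and effect size and on a falls variance inflation factor. Nor are they type I error rates: when raw effects differ, the raw-scale null is false. The test then answers a different question from the one the plan reads into it.

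Finally, the same section describes ANCOVA-type models for the outcomes and promises effects with 95% CIs, so it goes too far to say that the secondary results will represent one instrument only. However, the plan does not promise each outcome's own effect when the interaction is non-significant.

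**Conclusion.** The concern holds in conditional form. The rule that moves from a non-significant interaction to one common effect is explicit. Without a common metric and direction, the test and the common effect both depend on units; that follows from the algebra and needs no assumption about the SDs. The size cannot be determined from the document and ranges from negligible, at equal SDs and matching direction, to the illustrative 37% at a ratio of 2 with effects of 0.3 SD. Smaller effects or fewer residents with PROMIS give lower figures.

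Separately, with no power calculated for these outcomes, non-significance is weak grounds for a single effect even after standardisation. The point should be settled before analysis. It concerns a joint model for secondary outcomes and leaves the falls analysis and its sample size untouched.

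**What to change.** Amend the Statistical models section as follows:

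1. Name the FTQ score that enters the joint model (Response, Affect or Total; sum or item mean) and the PROMIS score.
2. Align direction, for example so that higher is worse on both.
3. Divide each outcome by a pre-specified SD before stacking. The pooled baseline SD is one acceptable choice.
4. Allow domain-specific variances in the joint model.
5. Report both outcome-specific effects with 95% CIs in every case, beside any standardised pooled effect. Keep the interaction as a description, with its alpha stated, and do not use its p-value to choose what is reported.

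The cost is one data step and a few sentences in the SAP. No new data are needed.
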